5 STATISTICAL METHODS

5.1 Sample Size Justification

Approximately 1415 patients will be screened to randomize 1200 subjects (approximately 600 per arm). If roughly 90% of the 600 subjects randomized to each treatment arm have a migraine treated with study medication in the allotted time period, there will be approximately 550 treated subjects per group.

Based on approximations from the Phase IIb study, 550 subjects provides more than 95% power to detect a difference between rimegepant and placebo on the subjects' freedom from their self-reported MBS. Also, based on the Phase IIb study, 550 subjects provides more than 95% power to detect a difference in freedom from pain at 2 hours post-dose. Having at least 95% power on each co-primary endpoint provides at least 90% power to detect a difference on both endpoints jointly.

5.2 General Statistical Methods and Data Handling

5.2.1 General Methods

All output will be incorporated into Microsoft Excel or Word files, sorted and labeled according to the International Conference on Harmonization (ICH) recommendations, and formatted to the appropriate page size(s). PDF versions of the output will also be produced.

Tabulations will be produced for appropriate demographic, baseline, efficacy, safety, and other parameters. For categorical variables, summary tabulations of the number and percentage within each category will be presented. If applicable, a category for missing data will also be presented. For continuous variables, n, mean, median, SD, minimum, and maximum values will be presented. The minimum and maximum values will be presented with the same precision as the data. The mean and median will be presented with the precision of the data + 1 decimal place. The SD will be presented with the precision of the data + 2 decimal places.

Formal statistical hypothesis testing and summary statistics will be presented, as well as confidence intervals (CIs) on selected endpoints, as described in the sections below.

The default tables, listings, and figures layout will be as presented in Table 4 below:

Orientation	Portrait	Landscape
Paper Size	Letter	Letter
Margins	Top: 3.05 cm Bottom: 2.54 cm Left: 2.54 cm Right: 2.54 cm	Top: 3.05 cm Bottom: 2.2 cm Left: 1.9 cm Right: 1.9 cm
Font	Table text: Times new Roman 9 or 10 pts Table title: Times new Roman 12 pts Table legend: Times new Roman 10 pts	Table text: Times new Roman 8, 9 or 10 pts Table title: Times new Roman 12 pts Table legend: Times new Roman 9 or 10 pts

The font size may be reduced as necessary to allow additional columns to be presented, but not at the expense of clarity. Also the orientation may be changed to portrait if appropriate.

5.2.2 Computing Environment

All statistical analyses will be performed using SAS statistical software (Version 9.2 or higher). Medical history and AEs will be coded using the Medical Dictionary for Regulatory Activities (MedDRA, Version 19.1). Concomitant medications will be coded using the World Health Organization Drug Dictionary (WHO-DD, Sep-2016).

5.2.3 Methods of Pooling Data

In the case of sparse data for the stratification factor (use of prophylactic medication: yes or no), the responses will be pooled in summary tables. Specific details on the procedures for pooling data are presented in the applicable sections of the document outlining the analyses.

5.2.4 Adjustments for Covariates and Stratification

The randomization of subjects was stratified by the use of prophylactic migraine medication (yes or no). Hence, most analyses are stratified by the use or prophylactic medication.

5.2.5 Multiple Comparisons

Type I error is controlled in this study by using a hierarchical gate-keeping procedure. First, the family of two co-primary endpoints is tested. If the co-primary endpoints are found to be significant, then secondary endpoints are tested in a fixed sequence. In particular, each co-primary endpoint will be tested for superiority to placebo at a two-sided alpha level of 0.05 without further adjustment for multiplicity. If the primary endpoint tests are both significant, then the following secondary endpoints will be tested in a fixed sequence, in the order shown, with each test conducted at p=0.05:

- 1. Photophobia Freedom at 2 hours
- 2. Phonophobia Freedom at 2 hours
- 3. Pain Relief at 2 hours
- 4. Nausea Freedom at 2 hours
- 5. Probability of Rescue Medication Use
- 6. Sustained Pain Freedom from 2 to 24 hours
- 7. Sustained Pain Relief from 2 to 24 hours
- 8. Sustained Pain Freedom from 2 to 48 hours
- 9. Sustained Pain Relief from 2 to 48 hours
- 10. Pain Relapse from 2 to 48 hours

11. Functional Disability at 2 hours

If a test in the hierarchy is not significant, then any further tests on endpoints in the sequence will have p-values presented only for descriptive purposes, and no conclusions will be drawn from those results.

For exploratory endpoints, no attempt will be made to adjust for multiplicity. Any exploratory endpoints for which p-values are produced will be evaluated at an unadjusted two-sided alpha level of 0.05 and presented only for descriptive purposes.

5.2.6 Subpopulations

The subgroups of interest for this study:

- Age: Categorized as $< 40, \ge 40$ years
- Race: white, black or African American, and other (certain tables may be created for the Asian population only; but in the subgroup analyses, Asian subjects will generally be included in the "other" category due to low counts)
- Sex: Female/Male
- Aura: Presence/Absence
- Headaches per Month: Categorized as < median, ≥ median
- Triptan Non-Responder: Yes/No
- CV Risk Contraindicating Triptans: Yes/No

Subgroup analyses will be performed for the primary endpoints only.

Triptan non-responders are identified using the "Prior Triptan Response" Case Report Form (CRF) pages. The definition of triptan non-responder is based on the number of triptans that a subject failed for efficacy reasons. For each triptan and route of administration, the subject is asked the questions shown in Table 5. A subject is considered to have failed a drug for efficacy reasons if they indicated "most or all of the time" for any of the reasons in the table.

A triptan non-responder is defined as any subject that fails two or more molecular entities for efficacy reasons. To be considered a failure for a molecular entity, the subject must have failed on all routes of administration that the subject tried for the molecular entity.

Table 5: Questions Used to Determine Triptan Non-response

	Most or All of the Time	Some of the Time	Rarely	Never
The treatment took too long to relieve my headache pain.				
The pain returned after it was relieved within 24 hours				
The treatment did not relieve my other symptoms (nausea, sensitivity to light or sound, for example).				
I could not count on this treatment to relieve my pain and symptoms every time				

Subjects with CV risk that contraindicates triptans are identified using the "Cardiac and Other Risk Factors" CRF pages. The pages are used to identify subjects with cardiovascular conditions cited in triptan labels as contraindications. A subject is identified as someone with cardiovascular risk factors contraindicating triptans if any of the following questions are answered as "yes":

- Does the subject have ischemic coronary artery disease?
- Does the subject have coronary artery vasospasm including Prinzmetal's angina?
- Does the subject have Wolff-Parkinson-White Syndrome or arrhythmias associated with other cardiac accessory conduction pathway disorders?
- Does the subject have history of stroke or transient ischemic attack (TIA)?
- Does the subject have peripheral vascular disease (PVD)?
- Does the subject have ischemic bowel disease?
- Does the subject have uncontrolled hypertension?

5.2.7 Re-Screened and Re-Randomized Subjects

In the event a subject is re-screened, then the data from the last screening visit, and latest laboratory assessment are used for the screening data.

In the event a subject is re-randomized, the subject will not be analyzed as part of the mITT population for the efficacy analyses. For safety, all AEs that occurred after the first date of randomization will be considered on-study.

For safety analyses, the subject will have their actual treatment assigned as BHV-3000 if at least one of their treatments was with BHV-3000.

5.2.8 Missing and Partial Dates

For efficacy analyses, partial or missing dates will not be imputed. The relative study days, where determined, will be calculated for full dates only.

For rescue medication, if the time of rescue medication is missing, then all endpoints on or after the date of rescue medication will be imputed as failures.

For missing and/or partial dates regarding concomitant/prior medications, a conservative approach will be taken. The medication will be assumed to be concomitant if it cannot be definitively shown that the medication was not taken after the period beginning 14 days prior to the taking of study medication.

If the start date of an AE is partially or completely missing, then the date will be compared as far as possible with the date of the randomization. The AE will be assumed to be on-study if it cannot be definitively shown that the AE did not occur or worsen during the post-randomization period (worst case approach).

The following general rules will be used:

- If the start day is missing, but the start month and year are complete, an AE will only be excluded as being on-study if the start month/year is before the month/year of randomization or if the stop date is before randomization.
- If the start day and month are missing, but the start year is complete, an AE will only be excluded as being on-study if start year is before the year of randomization or if the stop date is before randomization.
- If the start date is completely missing, an AE will be considered on-study unless the stop date is before randomization.

5.2.9 Visit Windows

Windows for the timeframe around efficacy measurements (15, 30, 45, 60, 90 minutes, 2, 3, 4, 6, 8, 24, and 48 hours) will be automated and captured in the eDiary. Refer to Table 6 for details on the evaluation intervals and Appendix 1 for details on the schedule of assessments.

Evaluation Protocol-Specified Interval		Analysis-Specified Interval		
Screening Phase				
Screening	Day -28 to Day -3	Day -40 to Day -3		
Acute (Randomization) Phase				
Baseline (Randomization)	Day 1	Day -2 to 1		
Onset of Migraine	Day 1 to 45	Day 1 to 45		
15, 30, 45, 60, 90 minutes post- dose	Time of Dose + 15, 30, 45, 60, and 90 minutes	Time of Dose + 15, 30, 45, 60, and 90 minutes (as captured in eDiary)		
2 hours post-dose	Time of Dose + 2 hours	Time of Dose + 2 hours (as captured in eDiary)		
8 hours post-dose	Time of Dose + 8 hours	Time of Dose + 8 hours (as captured in eDiary)		
24 hours post-dose	Time of Dose + 24 hours	Time of Dose + 24 hours (as captured in eDiary)		
48 hours post-dose	Time of Dose + 48 hours	Time of Dose + 48 hours (as captured in eDiary)		
End of Treatment Visit	Time of Dose + 7 days	Time of Dose $+ 2$ to 21 days		

Table 6: Evaluation Intervals for Efficacy Analysis

5.3 Planned Analyses

The analyses planned for endpoints that use data from this study only will be conducted after the last subject completes their End of Treatment Visit or discontinues from the study, and the database has been locked.

A meta-analysis of the durability endpoints will be conducted after the last subject in BHV3000-301 and BHV3000-302 completes their End of Treatment Visit or discontinues from the study, and both databases have been locked.

5.4 Subject Disposition

[figure not shown]
A summary of subject disposition will be tabulated for all subjects by treatment group and overall. The disposition table will support the creation of a consort diagram, similar to that shown in Figure 1. The categories in the table will include:

- Number of subjects screened
 - Number of screened subjects excluded from the study and reason for exclusion
- Number of subjects randomized
 - Number of subjects not treated, and the reasons for not being treated

- o Number of subjects treated, and their status
 - Completed Study
 - Discontinued, and reasons for discontinuation
- Number of subjects in each analysis population
- Number of subjects who intend to continue on to the BHV-3000-201 study.

A by-subject listing of subject disposition information, including the reason for withdrawal, if applicable, will be presented.

Figure 2: Consort Diagram

5.5 Demographic and Baseline Characteristics

Demographic information, medical history, migraine history, cardiovascular risk factors, and prior/current triptan response will be summarized by treatment group and overall for the mITT population. A similar set of tables will be made for the treated population.

A separate set of demographic tabulations, including demographic information and migraine history, will be made for subjects enrolled but not randomized (overall only) and subjects randomized but not treated (by randomized treatment and overall).

Demographic and other baseline data will also be provided in by-subject data listings.

5.6 Missing Data Description

Descriptions and tabulations of missing data will only be concerned with the post-baseline time points required for computation of the primary and secondary endpoints. These include the time points measured from 2 hours through 48 hours post-dose (e.g.: 2, 3, 4, 6, 8, 24 and 48 hours). The other time points: 15, 30, 45, 60 and 90 minutes are only required for the exploratory endpoints. Also, some tabulations focus on the pain endpoint as that should be generally descriptive of the other efficacy endpoints.

The number and percentage of randomized subjects that were randomized but not treated will be tabulated by treatment group.

For the mITT population, the items below will be tabulated by treatment group and overall, and sub-tabulated by date of migraine onset relative to September 13, 2017 (date \leq 13-Sep-2017; date > 13-Sep-2017; overall). Hence, there are three subcategories tabulated within each of two treatment groups and overall.

- Number and percentage of subjects with missing pain data at each time point from 2 through 48 hours post-dose. The categories in this tabulation are not mutually exclusive as subjects may have missing data at multiple time points.
- Number and percentage of subjects with: no missing pain data; 1 missing time point, 2 missing time points, 3 missing time points, 4 missing time points, 5 missing time points, 6 missing time points, or 7 missing time points. The categories in this tabulation are mutually exclusive.
- The number and percentage of subjects with missing data on the following endpoints measured at 2-hours post-dose: pain, MBS, photophobia, phonophobia, nausea, and functional disability.

In addition, the number and percentage of mITT subjects with missing pain data at 2 hours postdose will be displayed by treatment group and overall within the categories of each of the following subgroups:

• Age: Categorized as $< 40 \text{ or } \ge 40 \text{ years}$

- Race: white; black or African American; all other races combined (including Asian); Asian only
- Sex: Female or Male
- Aura for study migraine: Presence or Absence
- Headaches per Month: Categorized as < median or \ge median
- Triptan Non-Responder: Yes/No
- Rescue medication taken at anytime during the study: Yes/No
- MBS at migraine onset: photophobia, phonophobia, nausea, and not reported

5.7 Efficacy Evaluation

Unless otherwise noted, all efficacy analyses will be conducted using the mITT population as outlined below. All efficacy data will be included in listings by subject, study medication, and time point (as applicable). For efficacy analyses, baseline is considered as the assessment at the onset of the treated migraine. Subjects who were randomized twice will not be included in the efficacy evaluation.

5.7.1 Rescue Medication

Subjects who take rescue medication as recorded on the CRF or any medication used for headaches as recorded anywhere on the CRF or eDiary will be considered as failures for any efficacy evaluations that are coincident or follow the administration of the rescue medication/other headache medication. If the time of rescue medication is missing, subjects will be considered as failures for any efficacy evaluations are on or after the date of administration of the rescue medication/other headache medication/other headache medication.

5.7.2 MBS Recored After IP is Taken

Subjects that record their MBS after taking the investigation product (IP) are considered failures for the analysis of MBS.

5.7.3 Primary Efficacy Endpoints

In addition to the analyses described below, data regarding the co-primary efficacy endpoints, pain freedom and freedom from MBS at 2 hours post-dose, will be presented in a listing that includes treatment group, historical MBS, MBS at time of onset of study migraine, initial migraine severity, gender, presence or absence of aura, and use of prophylactic migraine medication.

5.7.3.1 Pain Freedom at 2 Hours Post-Dose

Pain freedom is assessed using the number of mITT subjects that report pain levels of "none" at 2 hours post-dose on a 4-point Likert scale (0=none, 1=mild, 2=moderate, 3=severe). The information from the 4-point scale is directly summarized as follows:

- A table showing descriptive statistics for the observed data, which includes the number and percentage of subjects reporting each of the 4 pain levels at 2 hours post-dose, and the percentage of subjects with missing data, for each treatment group. The table will include exact (Clopper-Pearson) 95% CIs for each percentage.
 - This table will be repeated for Asian subjects only.

The estimand for the primary analysis is the percentage of pain free subjects. In statistical terms, this percentage is arrived at by estimating the probability or the "risk" that a subject is pain free.

The population summary, the between group difference in the percentage of pain free subjects is assessed by computing the "risk difference" between treatment groups. This is evaluated by computing the common risk difference, using Cochran-Mantel-Haenszel (CMH) weights (sample size weights), stratified by the use of prophylactic migraine medication (yes or no). The risk difference is tested at a two-sided alpha level of 0.05. Missing data at 2 hours post-dose will be imputed as failures (NC=F). If a stratum (prophylactic medication use: yes or no) has sparse data (less than 5 subjects), then the strata will be pooled.

Results presented for the primary analysis include the following:

- The number and percentage of subjects who are pain free, and those not pain free, at 2 hours post-dose. These are presented by stratum and treatment group, with asymptotic standard errors (ASE), and 95% asymptotic CIs.
- Common risk difference with sample size, p-value, asymptotic standard error (ASE), and 95% asymptotic CIs.
- Risk difference within each strata with sample size, p-value, asymptotic standard error (ASE), and 95% asymptotic CIs.
- A plot of the risk differences within each strata, and common risk difference (similar to the risk difference plot produced by SAS Proc Freq).
- Common risk for each treatment with sample size, ASE, and 95% asymptotic CIs.

The primary analysis will be repeated for the subgroups described in Section 5.2.6.

Sensitivity analyses will be conducted as follows:

- 1. The primary analysis is repeated, once using the mITT subjects that had a qualifying migraine before the last relevant software fix was applied to the eDiaries (onset on or before 13-Sep-2017), and once for mITT subjects with migraine onset dates after the software fix was applied (onset after 13-Sep-2017).
- 2. The primary analysis is repeated, using the mITT population, with missing data at 2 hours post-dose imputed using Last Observation Carried Forward (LOCF). Baseline Observation Carried Forward (BOCF) is permitted.
- 3. The primary analysis is repeated using only data from complete cases (data present at baseline and 2 hours).
- 4. The primary analysis is executed using the mITT population, and multiple imputation (with 20 imputations; m=20) methods to impute missing data at 2 hours post-dose using the copy from reference approach. The fully conditional specification (FCS) method is used with a generalized logit distribution. Covariates may include use of prophylactic medication (yes or no), sex, migraine intensity at onset (severe or other), migraines per month (< median, ≥ median), date of migraine onset (on or before 13-Sep-2017 or after 13-Sep-2017), and the subject's MBS at time of study migraine onset (nausea, photophobia, or phonophobia).

- 5. A series of "what if" analyses are conducted that show what the analysis results would look like if the missing data in each treatment group were replaced with data from subjects having success rates that vary over the range of 0, 10, 20 and 30 percent. This analysis is presented in a 4x4 matrix, with the rows representing the success rates for the placebo group and the columns representing the success rates for the BHV-3000 group. For example, the "30,0" cell shows the hypothetical results when a responder rate of 30% replaces the missing placebo data, and a responder rate of 0% replaces the missing BHV-3000 data. Each cell in this table will show the common risk difference, asymptotic 95% CI and uncorrected p-value. The table will be accompanied by a forest plot that displays the 16 CIs.

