2.2 Randomization Methodology

The study will randomize approximately 1,200 subjects. The subjects will be randomized in a 1:1 ratio to receive rimegepant in a 75 mg tablet or matching placebo (see Figure 1). The randomization will be stratified by the use of prophylactic migraine medications (yes or no).

Figure 1: Study Schematic

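### The co-primary analyses are valid but leave out moderate/severe pain at onset; adding it as a stratum would bring a small gain in precision if severity is prognostic

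*SAP*

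**What the plan says.** **Analysis.** SAP 5.7.3.1 evaluates pain freedom by a common risk difference with CMH weights, "stratified by the use of prophylactic migraine medication (yes or no"). "The risk difference is tested at a two-sided alpha level of 0.05". SAP 5.7.3.2 uses the same method for MBS, and protocol 9.4.1 names the same single stratum for both endpoints. SAP 5.2.4 gives the reason: prophylaxis was the randomisation stratum.

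**Severity at onset.** The diary records headache intensity before and at dosing (protocol 4.3.2), and mITT membership requires a moderate or severe baseline attack (SAP 4.1). The SAP then uses severity in two places:

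- as a column, "initial migraine severity", in the listing of co-primary data (5.7.3);
- as "migraine intensity at onset (severe or other"), one of six covariates that may enter the multiple imputation model (sensitivity analysis 4 for each co-primary).

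It is not a stratum, a subgroup (5.2.6) or the basis of an adjusted sensitivity analysis. MBS sensitivity analysis 6 adds a stratum for the reported symptom; neither endpoint has a counterpart for severity.

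**Size.** "The subjects will be randomized in a 1:1 ratio" (SAP 2.2), "there will be approximately 550 treated subjects per group", and "550 subjects provides more than 95% power to detect a difference in freedom from pain at 2 hours" (SAP 5.1).

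**The concern.** Pain freedom is scored on the same four-point scale that gives severity at onset, and the plan already considers severity useful enough to help impute missing 2-hour outcomes. A variable of that kind is a natural candidate for adjusting the observed outcomes. Leaving it out can cost precision, and a chance difference in severity between arms then stays in the estimate.

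At stake is the width of the confidence intervals. The eleven secondary tests run in a fixed sequence (SAP 5.2.5), so one narrow miss makes every later p-value descriptive. That is where a small gain has most use.

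**Working it through.** **Inputs from the documents.** Two-sided alpha 0.05; 1:1 allocation; about n = 550 analysed per arm; Phase IIb pain freedom 31.4% against 15.3% (protocol 1.4.2). SAP 5.1 reasons "If roughly 90% of the 600 subjects randomized to each treatment arm have a migraine treated with study medication"; 90% of 600 is 540, close enough to 550 not to matter here.

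**Assumed, because the documents give nothing.** Share severe w = 20-50%; gap in pain freedom between moderate and severe attacks g1 = 5-20 points on rimegepant. On placebo, g0 is either proportional, g1 × 0.153/0.314, or equal to g1.

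**1. The plan's own figure.** For two proportions (pooled variance under the null), 31.4% against 15.3% at 550 per arm gives power above 99.9% (99.9995%; 99.9994% at 540). About 177 per arm would give 95%. The documents give no MBS rate. The Phase IIb symptom rates as proxies give 99.98% (nausea) or more. The stated power of more than 95% is reproduced.

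**2. Standard error without severity.** 
SE = √[(p1q1 + p0q0)/n] = √[(0.2154 + 0.1296)/550] = √(0.3450/550) = 0.02505.

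**3. Variance removed by a severity stratum.** Stratifying removes w(1−w)g² from each arm's binomial variance, with stratum weights taken as fixed, as the reported standard error does: 
R = w(1−w)(g1² + g0²)/0.3450, and the CI narrows by 1 − √(1−R).

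| Severe share | Gap, active arm | R, placebo gap proportional | R, placebo gap equal | CI narrower by |
|---|---|---|---|---|
| 20% | 5 points | 0.14% | 0.23% | about 0.1% |
| 30% | 10 points | 0.75% | 1.2% | 0.4-0.6% |
| 50% | 20 points | 3.6% | 5.8% | 1.8-2.9% |

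For the middle row, 0.21 × (0.0100 + 0.00237)/0.3450 = 0.75%. The subjects saved at equal precision are 1,100 × R, about 8 to 13. In the last row SE falls to 0.0246 or 0.0243.

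**4. Larger gaps.** Suppose severe attacks have one half to one third of the moderate rate.

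- 30% severe, ratio one half: moderate rate 0.314/0.85 = 36.9%, gap 18.5 points (placebo 9.0). R = 0.21 × (0.0341 + 0.0081)/0.3450 = 2.6%, or 14 of 550 per arm.
- 50% severe, ratio one third: gap 31.4 points (placebo 15.3). R = 0.25 × (0.0986 + 0.0234)/0.3450 = 8.8%, or 49 of 550 per arm, with the CI 4.5% narrower.

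Reaching 9% therefore needs an active-arm gap of about 31 points.

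**5. Where power is not saturated.** Take 22.35% against 15.3%, an effect of about 7 points. SE = √[(0.1735 + 0.1296)/550] = 0.02348, and power = Φ(0.0705/0.02348 − 1.96) = 85.2%. Over the grid in step 3 it rises to between 85.2% and 86.8% with a proportional placebo gap, and to about 87.4% at the extreme with an equal one.

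**6. Pain relief at 2 hours.** At 72.1% against 51.2%, total variance is 0.2012 + 0.2499 = 0.4510. A gap of 15 points in both arms with 30% severe gives 0.21 × 2 × 0.0225/0.4510 = 2.1%; 25 points with 50% severe gives 6.9%.

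**7. Chance imbalance.** A 2-SD difference in severe share is 2√[2w(1−w)/550] = 5.5 points (w = 30%) to 6.0 points (w = 50%). With a 15-point gap the risk difference shifts by 0.8-0.9 points, about one third of its 2.5-point standard error.

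**8. Type I error.** In simulation (20,000 trials per scenario, 20% on prophylaxis assumed), rejection under the null was 5.1% with and without the severity stratum.

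**The case against.** The strongest reply is that the plan contains no error. The analysis follows the only randomisation factor, protocol and SAP agree, and type I error is held. The restraint looks deliberate: the protocol's summary of changes records that the symptom stratum was removed from the MBS test, and the SAP carries it as a sensitivity analysis. All of this stands.

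A reader might go further and infer any of the following. The documents support none of them.

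- **Severity is an established predictor of response.** No section says so or gives rates by severity. Optional use in an imputation model shows only that it was thought possibly relevant.
- **The present choice has no benefit.** It is simple, prespecified, matched to the randomisation and keeps strata large.
- **Randomisation leaves severity unbalanced.** It balances severity in expectation. Severity could not have been a randomisation stratum, because the attack comes up to 45 days later.
- **Severity is always a pre-dose report.** SAP 6.1 plans to count subjects who took the drug before giving baseline migraine characteristics, and the mITT definition does not exclude them.

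Three practical objections also stand. The pooling rule covers only the two prophylaxis strata. Protocol 9.4.1 fixes the same stratification, so changing the SAP alone would create a mismatch. Pain relapse is unsuitable: at 15.3% of 550 about 84 placebo subjects enter it. With 10-20% on prophylaxis and the severity assumptions of step 4 (30-50% severe), its smallest cell would hold about 1 to 6.

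In the full mITT set sparse cells are not a serious obstacle: even 10% on prophylaxis and 20% severe leaves 550 × 0.10 × 0.20 = 11 per arm.

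**Conclusion.** The point holds as a minor improvement and does not show a defect. The co-primary tests are valid without severity. If severity is prognostic, stratifying by it reduces the variance of the pain-freedom risk difference by about 0.1-6% over 20-50% severe and gaps of 5-20 points, and by up to about 9% with gaps near 31 points. The severe share and the gap are assumptions, and the documents give no basis for preferring one part of the range. No figure can be given for MBS or functional disability, for which the documents state no planning rates.

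For the co-primaries at the planning rates the gain is of little consequence. For later tests with smaller effects it is worth up to about 2 percentage points of power in the example above. A reader should not conclude that the trial is underpowered or its primary result biased.

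**What to change.** **If the data are still blinded:**

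- Amend protocol 9.4.1, SAP 5.7.3.1 and 5.7.3.2, and the sections on the mITT-wide pain and functional endpoints, so that the CMH-weighted common risk difference is taken over prophylaxis × severity at onset (four strata). Leave pain relapse as it is.
- Reword the pooling rule: if any of the four cells has fewer than 5 subjects, collapse to prophylaxis only.
- State how subjects who reported severity only after dosing are handled.

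**If unblinding has occurred:** keep the primary analysis. Add the severity-stratified version as a sensitivity analysis for both co-primaries, parallel to MBS sensitivity analysis 6 and labelled post hoc. SAP section 7 and Appendix 3 describe supportive analyses in the past tense, so the timing must be settled first.

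**Cost:** no new data; some protocol and SAP wording, and smaller strata.

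### The sparse-data rule keeps strata of 5 or more subjects, where asymptotic 95% intervals can collapse or under-cover; strata in small subgroups are exposed, the primary tests are not

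*SAP*

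**What the plan says.** SAP 5.7.3.1 estimates pain freedom at 2 hours by a common risk difference with CMH weights, stratified by prophylactic medication. Its sparse-data rule reads: "If a stratum (prophylactic medication use: yes or no) has sparse data (less than 5 subjects), then the strata will be pooled". No threshold is given per arm or per number of responders.

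Three outputs follow for each retained stratum:
- Counts and percentages: "These are presented by stratum and treatment group, with asymptotic standard errors (ASE), and 95% asymptotic CIs".
- The difference: "Risk difference within each strata with sample size, p-value, asymptotic standard error (ASE), and 95% asymptotic CIs".
- A display: "A plot of the risk differences within each strata, and common risk difference (similar to the risk difference plot produced by SAS Proc Freq").

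The section then adds: "The primary analysis will be repeated for the subgroups described in Section 5.2.6". One of those subgroups is "CV Risk Contraindicating Triptans: Yes/No". SAP 5.2.6 sets no minimum subgroup size, although it folds Asian subjects into a residual race "category due to low counts".

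SAP 5.7.3.2 carries the pooling rule, the outputs and the subgroup repetition over to MBS. The pooling rule also recurs in 5.7.4.1 and 5.7.5. Exact Clopper-Pearson intervals appear in 5.7.3.1 only for the observed-data table of the four pain levels.

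**The concern.** The rule admits strata too small for the interval that is then applied to them. A stratum of 5 subjects in total may have two in one arm and three in the other. A Wald standard error is zero whenever an arm has 0% or 100% responders, and at these sizes that is common. If both arms are in that state, the interval for the risk difference has zero width.

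A table or plot would then show an interval labelled 95% that is a single point resting on a handful of subjects. The overall strata are unlikely to be that small with about 550 treated per arm, though the prophylaxis share is not given. Strata within subgroups are the likelier place. The CV-risk subgroup is a candidate: protocol 5.3 excludes uncontrolled, unstable or recently diagnosed cardiovascular disease, and it excludes uncontrolled hypertension, which is one of the seven conditions that define the subgroup in SAP 5.2.6. Protocol 1.4 bases much of the unmet need on patients who cannot take triptans, so readers will look at that display.

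**Working it through.** **Inputs.** Pain freedom 31.4% vs 15.3% (protocol 1.3.2.8), 1:1 allocation (SAP 2.2), two-sided 0.05 (SAP 5.7.3.1). Stratum and subgroup sizes are assumptions, because the documents give none.

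**The plan's own figure.** SAP 5.1 states more than 95% power with 550 per group and gives no coverage figure. The pooled rate is (0.314 + 0.153)/2 = 0.2335.
- SE under the null = √(2 × 0.2335 × 0.7665/550) = 0.02551
- SE under the alternative = √((0.314 × 0.686 + 0.153 × 0.847)/550) = 0.02505
- z = (0.161 − 1.96 × 0.02551)/0.02505 = 4.43, so power is 99.9995%

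The stated bound is met with these rates.

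**Within-stratum risk difference.** The Wald interval is d ± 1.96·√(a(1−a)/n₁ + b(1−b)/n₂), where a and b are the observed proportions in the rimegepant and placebo arms. Coverage is the summed binomial probability of all outcomes whose interval contains 0.161. Zero width needs both arms at 0% or 100%:
- 2 vs 3: (0.686² + 0.314²)(0.847³ + 0.153³) = 0.5692 × 0.6112 = 0.348
- 3 vs 2: (0.686³ + 0.314³)(0.847² + 0.153²) = 0.3538 × 0.7408 = 0.262

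Newcombe limits combine the Wilson limits (l, u) of the two arms: d − √((a−l₁)² + (u₂−b)²) and d + √((u₁−a)² + (b−l₂)²).

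| Rimegepant vs placebo | Wald coverage | Zero width | Newcombe coverage |
|---|---|---|---|
| 2 vs 3 | 62.4% | 34.8% | 97.0% |
| 3 vs 2 | 72.8% | 26.2% | 98.2% |
| 3 vs 3 | 76.3% | 21.6% | 95.9% |
| 5 vs 5 | 75.7% | 6.8% | 95.6% |
| 10 vs 10 | 91.6% | 0.4% | 95.0% |
| 25 vs 25 | 93.8% | about 0 | 95.4% |
| 50 vs 50 | 94.6% | about 0 | 95.2% |

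**Stratum-by-arm percentage.** The same enumeration for p ± 1.96·√(p(1−p)/n). Here zero width needs only the one arm at 0% or 100%; for n = 5 at 15.3% the chance is 0.847⁵ + 0.153⁵ = 0.436.

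| n in arm | Wald coverage / zero width at 15.3% | Wald coverage / zero width at 31.4% | Wilson coverage (15.3%; 31.4%) |
|---|---|---|---|
| 3 | 38.9% / 61.1% | 64.6% / 35.4% | 93.7%; 96.9% |
| 5 | 53.6% / 43.6% | 81.2% / 15.5% | 97.2%; 96.4% |
| 10 | 79.9% / 19.0% | 85.7% / 2.3% | 94.7%; 96.3% |
| 25 | 90.4% / 1.6% | 90.6% / 0.01% | 95.6%; 95.0% |
| 50 | 94.4% / 0.02% | 92.6% / about 0 | 95.3%; 95.3% |

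**Common risk difference in a subgroup.** Weights w = n₁n₂/(n₁+n₂) over the two prophylaxis strata, 400,000 simulated trials at 31.4% vs 15.3%. Strata of 10 and 3 per arm give 91.4% coverage, 15 and 3 give 92.3%, 20 and 5 give 93.5%, and 45 and 5 give 94.2%. With both arms at 15.3% the same layouts give 90.0% to 94.3%.

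**Full trial.** With 550 per arm and a smaller stratum of 3 to 110 per arm, coverage is 94.9% to 95.0% and type I error 5.0% to 5.1%.

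**MBS.** No Phase 2b MBS rate is given. Taking the photophobia, phonophobia and nausea rates of protocol 1.4.2 as an assumed range, Wald risk-difference coverage is 82% to 87% at 3 per arm, 83% to 89% at 5, 90% to 93% at 10 and about 94% at 25.

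**Empty arm.** With independent 1:1 assignment, a stratum of exactly 5 has an empty arm with probability 2 × 0.5⁵ = 6.25%. The rule would keep it although no difference can be estimated.

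**The case against.** The strongest objection concerns scope. A subgroup's own result is the common risk difference over both strata, not the result of one tiny stratum. A reader might infer that the subgroup forest plots are badly too narrow in general. The simulation does not support that: coverage is about 91% to 94% in modest subgroups at the planning rates. The large failures belong to small strata inside a subgroup, or to a subgroup so small that its whole sample resembles the upper rows of the first table. This objection stands.

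A reader might also infer that the CV-risk cells will certainly be tiny. The documents do not show it. Protocol 1.4.1 intends to enrol patients with cardiovascular conditions, protocol 5.2 admits patients with triptan contraindications, and stable disease is not excluded as such. Only the possibility can be claimed.

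These displays carry no confirmatory weight: SAP 5.2.5 controls error for the co-primary endpoints and the fixed sequence only. Sample sizes are printed beside each stratum difference, so an alert reader can see a degenerate interval for what it is. A missing difference from an empty arm is visible rather than misleading. All of this limits the consequence, but it does not make an interval labelled 95% correct.

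The SAP does not use the word Wald. It says asymptotic, with an ASE and a Proc Freq style plot, and Wald is the ordinary reading. If a score interval is meant, saying so settles the point for the risk differences.

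**Conclusion.** The point holds for descriptive displays in small cells. At sizes the pooling rule retains, the within-stratum interval for the risk difference can cover as little as 62% to 73% at a 2 vs 3 or 3 vs 2 split, with zero width in about a quarter to a third of cases. Coverage is still 76% at twice the threshold (5 per arm). It reaches 92% at 10 per arm and 94% at 25. The intervals for single-arm percentages are worse and recover more slowly, at about 90% with 25 subjects in the arm.

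A reader might infer that the co-primary result is at risk. It is not: full-trial coverage and type I error stay at their nominal values even with a very small second stratum.

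The conclusion rests on the Wald reading, on the Phase 2b rates for pain freedom (an assumed range for MBS), and on cell sizes that the documents do not report. The change is worth making before the subgroup tables are produced, and nothing confirmatory depends on it.

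**What to change.** In SAP 5.7.3.1, and by reference in 5.7.3.2 and wherever the same outputs are called for:
- Use Miettinen-Nurminen or Newcombe intervals for within-stratum risk differences, and for the risk difference in very small subgroups. Newcombe was enumerated above; Miettinen-Nurminen was not.
- Use Wilson or Clopper-Pearson intervals for stratum-by-arm percentages. Clopper-Pearson is already specified for the observed-data table.
- State that a stratum with no subjects in one arm is pooled, whatever its total.
- Leave the primary test and the common risk difference in all mITT subjects as planned.

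A further rule that suppresses strata below some count per arm is a matter of preference; the change of interval does not depend on it.

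The cost is a few lines of SAP text and a software option. SAP 5.2.2 allows SAS 9.2 or higher, so confirm that the release in use offers the chosen interval. No new data are needed. The downside is wider descriptive intervals in small cells.
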